## PROTOCOL SYNOPSIS

**Sponsor:** ProgenaBiome, LLC

**Title of Study:** PRG-044

**A Randomized, Double-Blind, Placebo-Controlled Phase IIa Study of Quintuple Therapy to Treat COVID-19 Infection**

**Study Centers:** 1

**Study Period:** 1 year

**Objectives:**

- Primary: to determine the efficacy of quintuple therapy against COVID-19 infection
- Secondary: To assess the safety and tolerability of treatment with quintuple therapy in Subjects with COVID-19 infection

**Study Design**

This is a Randomized, Double-Blind, Placebo-Controlled Phase II interventional study that will test the efficacy of quintuple therapy, HAZDpaC (Hydroxychloroquine, Azithromycin, Zinc, Vitamin D, and Vitamin C), in the treatment of Subjects with COVID-19 infection, compared to Subjects given only the vitamins, zinc (to put both groups into nutritional balance), and 2 placebos to match the hydroxychloroquine and azithromycin.

**Duration of Subject Participation (Study Visits)**

Subjects will be given the opportunity once diagnosis has been made via RT-PCR testing to participate. They may be recruited through the ProgenaBiome website, through a questionnaire. They may also be recruited through [www.clinicaltrials.gov](http://www.clinicaltrials.gov). Subjects may be referred by healthcare facilities. Subjects may also self-refer as well. All potential Subjects will be called during the recruitment process for screening assessments. The first step of this will be to obtain informed consent electronically, via the EDC. We will attempt to connect with these Subjects via Zoom/telemedicine. The validity of the test used to diagnose will be verified through medical records. (The diagnosis will be made by the Subject's evaluating physician or evaluation testing center, as part of the standard of care when infection is suspected). Following successful screening, Subjects will be randomized into the Arm 1 (treatment) or Arm 2 (placebo). At this time the associated treatment regimen will be prescribed and shipped to the Subject's home, along with home health equipment (MoMe Kardia II, thermometer, pulse oximeter and pregnancy test). Subjects will take azithromycin for 5 days, and hydroxychloroquine for 10 days, along with vitamin C, vitamin D, and zinc. Starting at Day 11 Subjects will discontinue hydroxychloroquine and reduce the doses of vitamin C, vitamin D, and zinc. The vitamin C, D, and zinc will be taken an additional 20 days at the reduced dose. Subjects will use the home EKG to transmit heart function information to the Study Team to be read by a board-certified cardiologist prior to dosing. The EKG will then be used daily for 10 days and results transmitted to the study team. Subjects will use a home pulse oximeter to monitor oxygen saturation and photographically report these values to the study team via the EDC. Subjects will track their symptoms using a daily diary (provided). Subjects will collect nasal or oropharyngeal swabs on Days 3, 5, 7, 14, and Month 1 and Month 3 for RT-PCR testing. Once Subjects have tested negative following treatment with HAZDpaC, Subjects will present to the clinic at 1, 2, and 3 months post-treatment for viral testing via RT-PCR. Alternatively, these visits may be conducted via videoconference and the subjects may collect these samples at home. At these visits blood will be drawn, a physical exam performed, and vital signs measured (optional). At the month 3 visit a pregnancy test will be given if applicable. Should Subject remain symptomatic at 2 weeks, or return to a positive state at any time during the trial they will be referred to their PCP by a phone call directly from the PI to the PCP. If at any time during the treatment phase or subsequent follow up Subject expresses and demonstrates a worsening or persistence of symptoms, they will be cared for according to standard of care or referred to their primary care provider, according to patient preference. The PI will discuss the case directly with that primary care provider. Subjects will continue to be followed for the remainder of the trial, and documentation of any additional treatments and Subject outcomes will be collected.

## Study Populations

### Inclusion Criteria

1. Informed consent provided electronically via the EDC, demonstrating that the subject understands the procedures required for the study and the purpose of the study
2. Male or female subjects 18 years of age and up
3. Subjects must agree to practice at least two highly effective methods of birth control for the duration of the study. This includes condoms with spermicide, oral birth control pills, contraceptive implants, intra-uterine devices, or diaphragms. At least one of these must be a barrier method. Subjects not of reproductive potential will be exempt (e.g. post-menopausal, surgically sterilized)
4. Diagnosis of COVID-19 by at least one of the following:
  - a. Physician diagnosis based on clinical presentation
  - b. Positive RT-PCR analysis
  - c. Positive rapid antigen test

### Exclusion Criteria

1. Refusal to provide informed consent
2. Pregnant or breastfeeding women
3. Diarrhea prior to infection
4. Negative test for COVID-19 by RT-PCR or rapid antigen test at screening
5. Any comorbidities which, in the opinion of the investigator, constitute health risk for the subject
6. Any contraindications for treatment with hydroxychloroquine
  - a. Hypoglycemic
  - b. Known G6PD deficiency
  - c. Porphyria
  - d. Anemia
  - e. Neutropenia
  - f. Alcoholism
  - g. Myasthenia gravis
  - h. Skeletal muscle disorders
  - i. Maculopathy
  - j. Changes in visual field
  - k. Liver disease
  - l. Psoriasis
  - m. History of QT interval >500msec
  - n. History of torsades de pointes
7. Anemia from pyruvate kinase and G6PD deficiencies
8. Abnormal EKG with QT prolongation acquired or from birth
9. Allergies to 4-Aminoquinolines
10. History of jaundice or high fevers prior to developing COVID-19
11. Treatment with any of the medications listed in Appendix II
12. Treatment with any other drug not listed that affects the QT interval
13. Treatment with any anti-epileptics

ProgenaBiome, LLC Protocol PRG-044	21 July2020
Number of Subjects	
Subjects will be enrolled to ensure that at least 600 complete the study. It is anticipated that screening of 1200 Subjects will be required to achieve this.	
Specimen Requirements:	
NP swabs (synthetic swab on plastic shaft) placed into 2-3mL of viral transport media. 1 mL of blood in an EDTA and 2 mL of serum in two serum separator tubes spun down	
Study Duration	
Screening of 1200 Subjects and enrollment of 600 Subjects is expected to take 3 months	

Primary Study Objective	Study Endpoints
The rate of recovery from COVID-19 in Subjects using Quintuple Therapy	Number of days from COVID-19 diagnosis to recovery via RT-PCR
Reduction or Progression of Symptomatic Days	Reduction and/or progression of symptomatic days, reduction of symptom severity
Secondary Objectives	Study Endpoints
Assess the safety and Tolerability of Quintuple Therapy	Assess the symptom response to study therapy as measured by the survey in the EDC
	EKG response, oxygen saturation, and vital signs at baseline, 2 weeks, 1 month, and two months
	Assess Adverse Events and Serious Adverse Events due to Quintuple Therapy

- a. Adverse event monitoring will be conducted for 12 weeks
- b. Serious adverse event monitoring will be conducted for 12 weeks
- c. Should any pregnancy occur, the pregnancy will be followed to its conclusion and the nature of that conclusion (termination, still birth, live birth, presence of absence of any birth defects) will be recorded. Any stillbirth or presence of any birth defects will be recorded as an SAE.

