  - Corneal changes including [edema](#) and opacities can be symptomless or may cause disturbances such as haloes, blurring of vision, or photophobia. They may be transient and are reversible when therapy is discontinued.
  - Maculopathies ,and macular degeneration (may be irreversible), extra-ocular muscle palsies (reversible), nystagmus
    - Maculopathies, and macular degeneration, can occur from 3 months to several years of exposure to this drug and may be irreversible
- Psychiatric
  - Affect lability
  - Nervousness
  - Psychosis
  - Suicidal behavior
- Respiratory
  - Bronchospasm
- Risks associated with azithromycin
  - Dermatologic
    - Generalized rash
    - Pruritis
    - Photosensitivity reaction
    - Stevens-Johnson syndrome
    - Urticaria
    - Dermatitis
    - Dry Skin
    - Hyperhidrosis
    - Eczema
    - DRESS
    - Toxic epidermal necrolysis
    - Erythema multiforme
    - Fungal dermatitis
    - Sweating
    - Vesiculobullous rash

- Maculopapular rash
- Gastrointestinal
  - Diarrhea
  - Nausea
  - Vomiting
  - Abdominal pain
  - Loose stools
  - Flatulence
  - Dyspepsia
  - Stomatitis
  - Gastroenteritis
  - Oral candidiasis
  - Constipation
  - Dysphagia/oral dysphagia
  - Abdominal distention
  - Dry mouth
  - Eructation
  - Mouth ulceration
  - Salivary hypersecretion
  - Pseudomembranous colitis
  - Pancreatitis
  - Tongue discoloration
  - Melena
  - Enteritis
  - Abnormal stools
  - Gastrointestinal disorders
  - Pyloric stenosis
- Genitourinary
  - Vaginitis
  - Vaginal infection
  - Dysuria
  - Intermenstrual bleeding
  - Testicular disorders
- Hematologic
  - Lymphopenia
  - Decreased hematocrit
  - Decreased hemoglobin
  - Neutropenia
  - Eosinophilia
  - Increased platelet count
  - Increased hematocrit
  - Increased lymphocytes
  - Increased basophils
  - Increased monocytes
  - Increased neutrophils
  - Thrombocytopenia
  - Anemia/Hemolytic anemia
  - Decreased platelet count
- Hepatic

- Hepatitis
- Increased AST, ALT, GGT, or blood bilirubin
- Hepatic failure
- Fulminant hepatitis
- Hepatic necrosis
- Hypersensitivity
  - Allergic reaction
  - Angioedema
  - Hypersensitivity
  - Anaphylactic reaction
- Immunologic
  - Moniliasis
  - Flu syndrome
- Metabolic
  - Decreased bicarbonate
  - Anorexia
  - Hyponatremia
  - Elevated alkaline phosphatase
  - Elevated bicarbonate
  - Hypochloridemia
  - Elevated lactate dehydrogenase
  - Hyponatremia
  - Hypokalemia
  - Dehydration
- Musculoskeletal
  - Arthralgia

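### No listed exclusion covers known hypersensitivity to azithromycin, one of the two randomised drugs; keeping such people out rests on a general screening clause with no prompt to check allergy history.

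*Combined protocol and SAP*

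**What the plan says.** The Study Design paragraph of the Protocol Synopsis has the control arm take the vitamins and zinc plus "2 placebos to match the hydroxychloroquine and azithromycin". The arms therefore differ by two drugs, hydroxychloroquine and azithromycin.

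The Exclusion Criteria appear twice, in the Synopsis and in Section 3. In both, item 6 is "Any contraindications for treatment with hydroxychloroquine", with fourteen sub-items (a to n), and item 9 is "Allergies to 4-Aminoquinolines". No item in either list names azithromycin or macrolides.

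Section 13.1 has its own block headed "Risks associated with azithromycin". Its entries include "Anaphylactic reaction", angioedema, Stevens-Johnson syndrome, toxic epidermal necrolysis, hepatitis and hepatic failure.

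Three other exclusions bear on the point:
- item 6k, "Liver disease";
- item 10, "History of jaundice or high fevers prior to developing COVID-19";
- item 5, "Any comorbidities which, in the opinion of the investigator, constitute health risk for the subject".

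The screening part of Section 3 adds a general clause. If the investigator's record review turns up a contraindication to taking part, no study drugs are supplied and the person is a screen failure.

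**The concern.** The plan includes a drug-allergy exclusion but writes it for the class of one randomised drug only. Its own risk list shows that the other can cause severe hypersensitivity. A site working down the numbered items would find nothing that stops a person with a documented earlier reaction to azithromycin.

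The setting makes this matter more. Subjects may self-refer or come through a website questionnaire, screening is by call or telemedicine, and the drugs are shipped home. On Day 1 a video call goes over dosing, and a cardiologist reads an EKG before dosing. Neither step would reveal a drug allergy unless someone asked. Eligibility screening is therefore the main protection against a foreseeable and possibly severe reaction.

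**Working it through.** The plan gives no figure on this point, so the check is a reading of every criterion against four kinds of person.

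1. **Known hypersensitivity to azithromycin or a macrolide.**
   - Items 6 and 9 do not apply, because they name hydroxychloroquine and 4-aminoquinolines.
   - Item 5 is worded for comorbidities, and a past drug reaction in an otherwise healthy person is not naturally one.
   - Item 11 concerns current treatment with drugs in Appendix 2. That list contains clarithromycin, erythromycin and telithromycin, but having once reacted to a drug is not being treated with it.
   - Only the general screening clause in Section 3 could catch this person.
2. **Past azithromycin liver reaction with jaundice.** Excluded by item 10, whatever the cause.
3. **Past azithromycin liver reaction with continuing liver disease.** Excluded by item 6k. It sits under the hydroxychloroquine heading but removes the person regardless of cause.
4. **Past azithromycin liver reaction that resolved without jaundice.** No listed item clearly applies. As in case 1, only the general clause could catch it.

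The next question is whether screening prompts anyone to look. Section 3 names prior and concomitant medications, the inclusion and exclusion criteria, vital signs, EKG recordings and oxygen saturation. The Schedule of Events in Section 6 adds demographics and a review of medical records. Neither names allergy history.

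For scale, the inputs are 600 subjects (the planned enrolment in the Synopsis), an assumed prevalence p of azithromycin or macrolide allergy of 0.5% to 2%, and assumed equal allocation, since no ratio is stated.
- Number passing the numbered list = 600 × p: 600 × 0.005 = 3, and 600 × 0.02 = 12.
- Number assigned azithromycin = half of that: 1.5 (about 2) to 6.

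Both ranges suppose that nobody is stopped by the general clause, by the prescriber or by their own refusal, so they are upper bounds. The finding rests on the wording of the criteria and does not depend on them.

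**The case against.** The strongest reply is the general clause in Section 3. It speaks of study drugs as a whole and is not limited to hydroxychloroquine. The review it belongs to also covers vital signs, EKG and oxygen saturation, so it is not confined to the numbered list. A documented azithromycin anaphylaxis found in the records would naturally count as a contraindication. This stands: a reader might infer that such a person is eligible under the protocol, and the documents do not support that. What they support is that exclusion depends on unprompted judgement for one randomised drug and on a written rule for the other.

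It is also fair to say that the lists are not blind to azithromycin's risks. Items 8 and 12, on QT prolongation and QT-affecting drugs, are not tied to hydroxychloroquine. Anemia, neutropenia, myasthenia gravis and liver disease are excluded under item 6 and also relate to risks that Section 13.1 gives for azithromycin. That narrows the gap to hypersensitivity and the small liver remainder in case 4.

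Finally, the recruitment questionnaire is not shown and the consent pages were removed, so allergy history may be asked there. Even so, neither the criteria nor the screening steps would tie the answer to a decision.

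**Conclusion.** The gap holds in a limited form. No numbered exclusion covers known azithromycin or macrolide hypersensitivity, or a past azithromycin liver reaction that resolved without jaundice, and the only safeguard is a general clause with no listed prompt. It should be corrected, because the foreseeable harm is serious and the change is small. The counts of 3 to 12, and about 2 to 6, are upper bounds resting on an assumed prevalence and assumed equal allocation.

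Three further inferences are tempting but unsupported:
- **Every prior azithromycin liver reaction is eligible.** Items 6k and 10 already remove those with liver disease or a history of jaundice.
- **Excluding such people on judgement biases the safety comparison.** Exclusion before randomisation would lower azithromycin-related events in the active arm, not raise them. Section 16 also plans no inferential safety analysis.
- **The supplements need the same change.** Section 13.1 lists allergic reactions to vitamins C and D and renal damage from zinc, but both arms take the supplements, and a listed risk alone shows no defect in eligibility.

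**What to change.** Reconcile the two exclusion lists (Synopsis and Section 3) with the general screening clause in Section 3 and the azithromycin risks in Section 13.1, so that the contraindication and allergy exclusions address both randomised drugs. The clinical wording, including how far it extends within the macrolide class and how past liver reactions are treated, is for the investigator to set. Name allergy and past drug-reaction history as something to check in the medical-record review already done at screening.

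The cost is a short amendment to items 6 and 9 in both lists and one line in the screening procedure. No new test or visit is needed. The downside is a few more screen failures, which on the assumptions above would be at most about 3 to 12 per 600 otherwise enrolled.

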## List of Abbreviations

AE	Adverse event
BP	Blood pressure
CFR	Code of Federal Regulations
CRF	Case report form
DNA	Deoxyribonucleic Acid
EDC	Electronic Data Capture
FDA	Food and Drug Administration
GCP	Good Clinical Practice
GI	Gastrointestinal
HIPAA	Health Information Portability and Accountability Act
HR	Heart Rate
ICF	Informed consent form
ICH	International Conference on Harmonization
IRB	Institutional Review Board
mL	Milliliters
NP	Nasopharyngeal
OP	Oropharyngeal
OTC	Over the counter
O 2 Sat	Oxygen Saturation
PI	Principal Investigator (at each site)
PPE	Personal Protective Equipment
RR	Respiratory Rate
Rx	Prescription medication
RNA	Ribonucleic Acid
RT-PCR	Reverse transcription polymerase chain reaction
SAE	Serious adverse event
WHO	World Health Organization

## 1. Background and Rationale

COVID-19 is a novel betacoronavirus, the origins of which are still being investigated, and which was first identified and isolated in Wuhan, China. This disease has rapidly spread to become a worldwide pandemic, as declared by the World Health Organization (WHO). Symptoms of COVID-19, including fever, myalgia, coughing, shortness of breath, headache, and GI symptoms may appear from 2 and 14 days after exposure. However, incubation may be longer. Approximately 20% of Subjects progress to severe illness, including pneumonia, respiratory distress, and even death. Cases in the US have increased exponentially over the last months. The disease is spreading rapidly, and a cure is desperately needed.

It is known that single anti-viral agents work poorly when used alone in other chronic viral infections such as Hepatitis C or HIV infection. So, we know that the greater number of anti-viral agents used in combination, the greater the cure rate.

It has been noted from recently published results that Hydroxychloroquine can be extremely effective against coronavirus and thousands of cures have been reported. Of particular interest are several studies out of China and two from France which indicate not only better survival but more rapid recovery and shorter time to viral clearance. The studies in France utilized a dose of 200mg of hydroxychloroquine TID for 10 days. Since the half-life of this drug is 20-80 days, we hypothesize that such large dose is not required for efficacy, and that a slightly lower dose will not only be effective, but will have fewer side effects.

Azithromycin, a commonly prescribed macrolide antibiotic for the past thirty years, has recently been used in clinical trials along with hydroxychloroquine for the treatment of COVID-19. It too has demonstrated an excellent safety profile. P. Gautret, D. Raoult, et al., recently published the results of an open labeled, nonrandomized clinical trial in 80 Subjects at the University Hospital Institute Mediterranean Infection in Marseille, France. Subjects were treated with hydroxychloroquine sulfate 200mg three times a day for 10 days and azithromycin 500mg on day 1 followed by 250mg per day on days 2-5. [name] found clinical improvement and favorable outcomes in all but two of the Subjects, and 93% had a negative nasopharyngeal viral load RT-PCR test by day 8. Virus cultures from Subject respiratory samples were negative in 97.5% of Subjects at Day 5. Subjects were monitored for QT prolongation and other adverse events. Adverse events were noted to be "rare and minor." Vitamin C has long been known to enhance the immune response of the host. It has also been shown to have direct antiviral effects, in both acute and chronic infections. Many studies have shown the enhancement of antimicrobial and natural killer cell activities, lymphocyte proliferation, chemotaxis, and delayed-type hypersensitivity. It protects cells from redox reactions and thus the reactive oxygen species generated during respiratory burst and inflammation.

Vitamin D has also been shown to have direct antiviral effects, and to enhance the efficacy of other antiviral treatments. Vitamin D levels have also been shown to be a predictor of treatment efficacy in Subjects with Hepatitis C viral infections. Vitamin D also downregulates the ACEII receptor which is the target of COVID-19 and as such is directly antiviral for this infection. In previous studies, doses have ranged from 160mg-1g (IU \* 0.67 = mg) Deficiency of zinc has been linked to impaired innate immune functions. Supplementation of zinc has been shown to shorten the duration of respiratory infections.

Many antiviral treatment studies have shown that drugs used in combination are more effective than single therapies. In short, the whole is greater than the sum of its parts. Thus, we hypothesize that a combination of drugs has greater therapeutic potential, and can be effective in preventing COVID-19. Reduction of the vitamin C, vitamin D, and zinc doses following treatment with hydroxychloroquine is designed to minimize side effects while maintaining their antiviral effects.

## 2. Trial Objectives

Primary Study Objective	Study Endpoints
The rate of recovery of mild or moderate COVID-19 in Subjects using Quintuple Therapy	Number of Days Recovery from COVID-19 diagnosis to Recover via RT-PCR
Secondary Objectives	Study Endpoints
Assess the safety of Quintuple Therapy	Assess the symptom response to study therapy as measured by the survey in the EDC
	EKG response, oxygen saturation, and vital signs at baseline, 2 weeks, 1 month, and two months
Assess Tolerability of Quintuple Therapy	Assess Adverse Events and Serious Adverse Events due to Quintuple Therapy

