- Temperature

- d. Subject will take prescribed regimen

Drug	AM Dose	PM Dose
Hydroxychloroquine (or Placebo)	200mg	200mg
Vitamin C	1500mg	1500mg
Vitamin D	1500IU	1500IU
Zinc	25mg	25mg

- o Day 11-Day 13

- a. Subject will complete AM/PM diaries

- b. Subject will take prescribed regimen

Drug	AM Dose	PM Dose
Vitamin C	750mg	750mg
Vitamin D	750IU	750IU
Zinc	12.5mg	12.5mg

- o Day 14

- a. Subject will be called

- Remind them to collect nasal or oropharyngeal swab
- Ask about AE/SAE
- Symptom resolution or progression
- Answer any questions the Subject may have

- b. Subject will collect nasal or oropharyngeal swab

- c. Subject will complete AM/PM diaries

- d. Subject will take prescribed regimen

Drug	AM Dose	PM Dose
Vitamin C	750mg	750mg

Vitamin D	750IU	750IU
Zinc	12.5mg	12.5mg

- Day 15-30
  - a. Subject will complete AM/PM diaries
  - b. Subject will take prescribed regimen

Drug	AM Dose	PM Dose
Vitamin C	750mg	750mg
Vitamin D	750IU	750IU
Zinc	12.5mg	12.5mg

- Follow-Up Period (These visits can be conducted via videoconference or in person)
  - Month 1 (outpatient only AFTER negative test)
    - a. Vital signs (BP, HR, RR, oxygen saturation, temperature)
    - b. Assessment for AE and SAE
    - c. EKG (Optional)
    - d. Physical exam (Optional)
    - e. Blood draw for CBC/Complete metabolic panel/C-Reactive Protein/Blood hydroxychloroquine levels/SARS-CoV Antibody test (All optional)
      - Blood HQ levels will remain blinded from all but unblinded coordinator
    - f. Update list of prior and concomitant medications
    - g. Study team will collect nasal or oropharyngeal swab (If patient elects to refrain from this in-person visit they will collect this at home)
  - Month 2 (outpatient)
    - a. Vital signs (BP, HR, RR, oxygen saturation, temperature)
    - b. Assessment for AE and SAE
    - c. EKG (Optional)
    - d. Physical exam (Optional)
    - e. Blood draw for CBC/Complete metabolic panel/C-Reactive Protein (Optional)
    - f. Update list of prior and concomitant medications
  - Month 3 (outpatient)
    - a. Vital signs (BP, HR, RR, oxygen saturation, temperature)
    - b. Assessment for AE and SAE
    - c. EKG (Optional)
    - d. Physical exam (Optional)
    - e. Blood draw for CBC/Complete metabolic panel/C-Reactive Protein (Optional)
    - f. Update list of prior and concomitant medications

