#### **11.6 Documentation and Methods of Detecting Adverse Events and Serious Adverse Events**

It is the responsibility of the investigator to document all AEs that occur during the study. Participants will be

evaluated and questioned generally for AEs during the course of the study, starting at the signing of the informed consent. Care will be taken not to introduce bias when detecting AEs and/or SAEs. Open-ended and non-leading verbal questioning of the participant is the preferred method to inquire about AE occurrences. All clearly related signs, symptoms which are either volunteered by participants or observed during or following the course of investigational product administration on the appropriate eCRF. AEs and SAEs reported from the signing of the ICF to the EOS visit are to be reported and documented on the AE eCRF. Any AE related to a protocol procedure should be marked as such on the eCRF.

All AEs spontaneously reported by the participant and/or in response to an open question from study personnel or revealed by observation, physical examination, or other diagnostic procedures will be recorded on the AE eCRF. Any clinically relevant changes in laboratory assessments or other clinical findings as are considered AEs and must be recorded on the AE eCRF. AEs are to be followed for resolution.

It is important that each AE report include a description of the event, duration (onset and resolution dates), severity, relationship with treatment, any other potential causal factors, any treatment given or other action taken (including dose modification or discontinuation of treatment), and outcome. In addition, SAEs should be identified and the appropriate seriousness criteria documented. AEs categorized as SAEs must also be documented within the appropriate SAE section in the eCRF or a paper SAE form if the system is down or otherwise unavailable. Note both methods should not be used beside each other, the paper is for back up reporting only.

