#### **11.7 Documentation and Detection of Adverse Events and Serious Adverse Events**

It is the responsibility of the investigator to document all AEs that occur during the study. Participants will be evaluated and questioned generally for AEs during the course of the study, starting at the signing of the informed consent. Care will be taken not to introduce bias when detecting AEs and/or SAEs. Open-ended and non-leading verbal questioning of the participant is the preferred method to inquire about AE occurrences. All clearly related signs, symptoms which are either volunteered by participants or observed during or following the course of investigational product administration on the appropriate eCRF. AEs and SAEs reported from the signing of the ICF to the EOS visit are to be reported and documented on the AE eCRF. Any AE related to a protocol procedure should be marked as such on the eCRF.

All AEs spontaneously reported by the participant and/or in response to an open question from study personnel or revealed by observation, physical examination, or other diagnostic procedures will be recorded on the AE eCRF. Any clinically relevant changes in laboratory assessments or other clinical findings as are considered AEs and must be recorded on the AE eCRF. AEs are to be followed for resolution.

It is important that each AE report include a description of the event, duration (onset and resolution dates), severity, relationship with study drugs, any other potential causal factors, any treatment given or other action taken (including dose modification or discontinuation of study), and outcome. In addition, SAEs should be identified and the appropriate seriousness criteria documented. AEs categorized as SAEs must also be documented within the appropriate SAE section in the eCRF or a paper SAE form if the system is down or otherwise unavailable as described in Section 8.3.4. Note both methods should not be used beside each other, the paper is for back up reporting only.

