## 16. Adverse Event Analysis

All adverse events and serious adverse events will be analyzed to determine likelihood of association with treatment. Likely and known Treatment Emergent Events will be tabulated and summarized by presenting the incidence number (number and percentage of subjects) in each treatment group. No inferential analyses will be performed on safety parameters.

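### Tolerability is measured only through adverse events attributed to treatment; nothing in the protocol commits to counting, by arm, how many subjects stop the randomised drugs early

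*Combined protocol and SAP*

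**What the plan says.** The synopsis sets the secondary objective as "To assess the safety and tolerability of treatment with quintuple therapy in Subjects with COVID-19 infection". Its endpoint table keeps safety and tolerability together ("Assess the safety and Tolerability of Quintuple Therapy") and lists symptom response, EKG, oxygen saturation and vital signs, and adverse events due to therapy.

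Section 2 splits the two. Symptom response and the EKG and vital-sign measures sit with safety. "Assess Tolerability of Quintuple Therapy" has its own row with a single endpoint, "Assess Adverse Events and Serious Adverse Events due to Quintuple Therapy".

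Stops of the randomised drugs are foreseen. Appendix 4 lists criteria for stopping individual subjects, and Appendix 3 names several side effects that lead to discontinuation.

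Part of the information is already collected. Section 11.6 requires each adverse event report to hold "any treatment given or other action taken (including dose modification or discontinuation of treatment), and outcome". Section 11.2 asks for the action taken with the product for every SAE. The opening of Section 11 makes an abnormal finding reportable if it leads to stopping treatment.

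On reporting, Section 16 says "Likely and known Treatment Emergent Events will be tabulated and summarized" by treatment group and rules out inferential analysis of safety. Section 15 lists PCR results, symptoms and symptom severity as its measurements. Neither section mentions early stopping.

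**The concern.** How many people could not, or did not, finish a course is the most direct measure of whether they tolerated it. Here that count is neither an endpoint nor a planned table. The endpoint that stands in for it passes through a causality judgement, so it can miss part of what it is meant to show.

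The drugs are shipped to the subject and taken at home. Section 3 tells subjects each day to take the regimen, but it describes no pill count or dose record, and it describes the diary as a record of symptoms. Whether a home dose was taken cannot be reconstructed later if nobody asked at the time. A table could still be added at the analysis stage, but only for stops that left a record.

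At stake is a tolerability conclusion drawn from attributed adverse events alone, which could look favourable even if noticeably more subjects stopped in one arm.

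**Working it through.** The plan gives no stopping rate or tolerability figure to reproduce, so the check is mainly a tracing of the text.

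**What happens to a stop under the plan as written**

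| Type of early stop | Recorded? | In the Section 16 by-arm table? | Counted as a stop? |
|---|---|---|---|
| Adverse event judged likely or known to be related | Yes (11.2, 11.6) | Yes, as an adverse event | No |
| Adverse event judged unrelated | Yes (11.2, 11.6) | No | No |
| Abnormal finding that led to stopping | Yes, as an adverse event (Section 11) | Only if judged related | No |
| Subject's choice, no adverse event | No field described | No | No |

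The last column is the same throughout. Suppose 10% of an assumed 300 subjects in one arm stop early: 300 × 0.10 = 30. If half of these stops follow events judged related, 30 × 0.5 = 15 subjects appear in the table as having an adverse event. If all do, 30 appear. In both cases the number shown as having stopped is 0.

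**A wording difference in the source field.** Section 11.6 refers to stopping treatment. The otherwise parallel sentence in Section 11.7 reads "including dose modification or discontinuation of study), and outcome". Stopping the drug and leaving the study are different facts, and a count taken from this field depends on which one was entered.

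**How informative a by-arm count would be.** The total of 600 comes from Section 15, whose formula reproduces: log(0.05)/log(0.995) = 597.647. It is used here only as the source of N. The allocation ratio is not stated, so 300 per arm is an assumption, and so are all the rates. With d = p1 − p2, SE = √[p1(1−p1)/300 + p2(1−p2)/300] and 95% CI = d ± 1.96 × SE:

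| Stopping rates | d (points) | Half-width (points) | 95% CI (points) |
|---|---|---|---|
| 5% vs 3% | 2 | 3.1 | −1.1 to 5.1 |
| 10% vs 5% | 5 | 4.2 | 0.8 to 9.2 |
| 15% vs 10% | 5 | 5.3 | −0.3 to 10.3 |
| 15% vs 5% | 10 | 4.7 | 5.3 to 14.7 |
| 20% vs 10% | 10 | 5.7 | 4.3 to 15.7 |

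First row in full: SE = √(0.05×0.95/300 + 0.03×0.97/300) = √0.000255 = 0.0160, and 1.96 × 0.0160 = 0.031.

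Over these rates the difference is estimated to within about 3 to 6 points. No change to the sample size is needed to make the count worth reporting.

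**The case against.** The strongest reply is that Section 15 defers further detail to a statistical analysis plan to be written before database lock, and disposition tables could be placed there. That is fair, and it limits the point to what the supplied protocol commits to. It does not remove the point: the endpoint is set in Section 2, and a later plan cannot recover home doses that were never recorded.

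A second reply is that other endpoints already speak to tolerability. The synopsis does add symptoms, EKG and vital signs, with no causality filter, and adverse event incidence by arm is a partial measure. A reader might therefore go further than this point does and infer that the trial cannot answer its tolerability question at all. The documents do not support that; the answer is incomplete, not absent. Still, the EKG and vital-sign endpoint is set at baseline, 2 weeks, 1 month and two months, while hydroxychloroquine/placebo ends on Day 10. No post-baseline time point of that endpoint falls within dosing, and none of these measures counts a stop.

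Third, the Section 16 wording might be read more broadly than as a causality filter. Even if every adverse event were tabulated, stops would still appear only as events.

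Fourth, the diary form is not among the documents, so it may already ask about doses. If it does, that part of the fix is already met.

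**Conclusion.** The point holds as a gap in the endpoint and its reporting, and it should be corrected. Section 2 measures tolerability only by attributed adverse events, Section 16 tabulates by arm only those judged likely or known, and no supplied section commits to a by-arm count of early stopping. That a poorly tolerated regimen could look tolerable is an inference about what the plan allows, not something the documents state.

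The size of any effect is unknown. The 3 to 6 point precision rests on an assumed 300 per arm and assumed rates of 3% to 20%, and two of the five intervals shown include zero. Three stronger readings are tempting and not supported:

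- **That a clear tolerability signal is being hidden.** The documents give no stopping rates, so a clear difference would follow only from the rates chosen.
- **That untaken drug dilutes the efficacy estimate by a calculable amount.** No rate of non-use is given, and someone who stops early has still taken part of the course.
- **That the Month 1 hydroxychloroquine level would fill the gap.** It is kept blinded ("Blood HQ levels will remain blinded from all but unblinded coordinator") and feeds no stated analysis. It is also optional and says nothing about azithromycin. Section 3 ties the Month 1 visit to a prior negative test, so those sampled would be selected on an outcome. The synopsis times the visit from the end of treatment, which Section 3 does not, and no assay limit is given.

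**What to change.** In Section 2, the synopsis and Section 16, add to the tolerability endpoint: the number and percentage of subjects in each arm who stop hydroxychloroquine/placebo or azithromycin/placebo before the planned last dose, by reason and regardless of judged causality.

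Take the count from the action-taken field of the adverse event record and from Appendix 4 stops. Add a dose-taken tick to the existing AM/PM diary for Days 1-10, so that stops without an adverse event are also captured.

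Reconcile Sections 11.6 and 11.7 so that stopping the drug is recorded separately from leaving the study.

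Report the result descriptively. Counts and percentages by arm and reason are enough to close the gap. If a two-sided 95% confidence interval for the difference is shown, label it as a descriptive exception to the Section 15 rule that intervals are one-sided and to the Section 16 rule against inferential safety analysis.

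The cost is an extended endpoint row, one summary table and slightly more diary burden for ten days. The fix changes no dose, stopping criterion or sample size.
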